### **6.3.10 Laboratory Evaluations**

Standard of care laboratory assessments for safety will be done at Screening, 2, 8, 10, and 16 month visits (visits 1, 5, 9, 11, and 14). All laboratory assessments will include: a TSH CBC with Hgb, Hct, RBC, WBC, MCV, MCH, MCHC, PLT, RDW-CV, neutrophils, lymphocytes, monocytes, eosinophils, and basophils, comprehensive metabolic profile (CMP) including sodium, glucose, potassium, BUN, creatinine, bicarbonate, chloride, total calcium, total bilirubin, ALP, AST, ALT, total protein, albumin, and cholesterol, and urine dipstick testing to test for glucose, bilirubin, ketones, specific gravity, blood, pH, protein, urobilinogen, nitrite, and leucocytes. If the safety blood samples cannot be collected at the screening visit, sites may collect them at the -2 month or baseline visits (v2 or v3) as long as it is prior to randomization. If the safety blood samples cannot be obtained at a visit occurring post-randomization (v5, 9, 11 and 14), then the sample may be collected at the next visit to the site.

When blood is drawn at the above visits the safety testing will be done first, followed by PK, followed by biomarkers in order of importance to subject protection and study conduct. Drawing of the blood tests will be ordered in this way because it may be challenging to get enough

volume for all the blood samples from children this age and the order will ensure the most important samples for patient safety are collected first.

Urine dipstick testing will be done by the coordinator or designated staff at the site. Urine dipstick testing will be done rather than a full urinalysis because there were no significant abnormalities in U/A values in any of the other Novartis studies in FXS, children tend to have less issues with kidney functions than the adults studied previously, and the children in this study will mostly not be toilet trained (larger volumes of urine which has to be collected in a urine bag may be challenging to obtain). If the urine dipstick indicates there may be a urinary infection, a full U/A and urine culture may be sent to the local lab at the site at the discretion of the investigator based on clinical assessment. In the event that a urinalysis is done by the local lab, it would be considered a clinical assessment, and not a study procedure. Urine dipstick supplies will be provided to sites by the PPI site as needed.

Urine dipstick testing should be completed during the screening visit when possible. If the urine dipstick testing cannot be completed at the screening visit, sites may collect them at the -2 month or baseline visits (v2 or v3) as long as it is prior to randomization. If the urine dipstick testing cannot be obtained at a visit occurring post-randomization (v5, 9, 11 and 14), then the sample may be collected at the next visit to the site. For more details please refer to the Manual of Operations.

Laboratory assessments will be drawn in standard specified tubes in the Study Lab Manual and samples shipped to the CLIA-certified CCC Central Laboratory at the University of Rochester where assays will be performed as per standard clinical testing. The CCC Central Laboratory will provide the specimen collection kits for safety tests (phlebotomy supplies, collection tubes, aliquot tubes, barcoded labels) and IATA compliant shipping materials for the sites to ship to the CCC Central lab. Study specific test requisitions with instructions for collecting, documenting, processing, and shipping will also be provided by the CCC Central lab. Fed Ex labels for shipping on a CCC Central lab account number will be provided to sites, and will allow tracking of shipments by the CCC Central lab to ensure timely delivery of samples and reporting of results. Instructions for obtaining, processing and sending safety labs to the CCC Central Laboratory will be provided in the manual from the CCC Central Laboratory at study initiation. All safety lab result reports will be sent to the sites where these will be maintained with the source documents.

The DCC will provide all relevant laboratories with online forms and/or electronic data exchange mechanisms - depending on their capabilities and needs - to enter, update and obtain relevant data. When a blood sample has been obtained, the clinical study site study coordinator will send the sample (participant ID, site ID, and protocol ID numbers will be used) to the University of Rochester Central Laboratory. Results will be sent via a secure system to University of Rochester laboratory with no individual-identifying information on the report. The laboratory will electronically communicate the test results to the respective clinical study sites in a secure manner. The laboratory will also transfer test results electronically to the DCC via an established data transfer mechanism.

The site investigator or an authorized sub-investigator must sign and date all laboratory results, indicating whether any out of range lab values are clinically significant (CS) or not clinically significant (NCS) on the lab report. The CTCAE (version 4.0) grading system for clinically significant abnormal lab values (laboratory adverse events) will be used. Clinically significant findings at screening will be discussed with the PPI and Study Team prior to enrolling the patient in the study. Clinically significant findings after starting study medication will be discussed with the PPI and Study Team to determine whether the subject should continue in the study.

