### 4.2 Exclusion Criteria

1. Use of medications impacting GABA, glutamate and/or mGluR5 pathway receptors or transmission.  
\*\*Note\*\* Treatment with acamprosate, amantadine, budipine, carbetocin, cycloserine, dextromethorphan, felbamate, ketamine, lithium\*, minocycline, memantine, oxytocin,

remacemide, racemic baclofen, riluzole, fycampa, investigational mGluR5 medications, and/or statins are exclusionary.

\*\*Note\*\* Lithium taken as a dietary supplement is permitted if the dose is less than 5mg/day. A 5mg/day dose is the recommended dietary intake level, and is therefore not considered to be therapeutic. Lithium dosage must remain the same throughout the duration of the trial, and documented in the concomitant medication log.

2. Unstable seizure disorder as defined by any seizure in the 6 months prior to the screening visit, and/or any change in anti-convulsant drug dosing in the 60 days prior to screening.  
\*\*Note\*\* Use of levetiracetam and oxcarbazepine are among permitted anticonvulsants.
3. Use of any other investigational drug at the time of enrollment or within 30 days or 5 half-lives (whichever is longer) of the investigational drug prior to screening until end of study visits (or longer if required by local regulations).
4. History of hypersensitivity to AFQ056 or any mGluR antagonist.
5. History or presence of any clinically significant disease of any major system organ class, within the past 2 years prior to screening including but not limited to neurological, cardiovascular, endocrine, metabolic, renal, or gastrointestinal disorders. This does not include typical features of FXS such as psychological symptoms or history of epileptic seizures.
6. Significant acute illness that did not completely resolve at least four weeks prior to the Screening visit.
7. Abnormal laboratory values at screening that are in the opinion of the investigator are clinically significant and may jeopardize the safety of the study subject.
8. Use of (or use within at least 5 half-lives before dosing) concomitant medications that are strong/moderate inhibitors or inducers of CYP1A1/2, CYP2C9/19 or CYP3A4 (see Appendix B).
9. Subjects who are, in the opinion of the investigator, unable to comply with the requirements of the study.
10. Presence of immunodeficiency diseases at the time of screening, based on medical history, including a positive HIV test result.

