#### **4.4.6 Randomization/Treatment Assignment**

If a subject is deemed eligible for enrollment into the study at the screening visit, that subject will be entered into the placebo lead-in. When he/she returns for the baseline visit 4 months later, the subject will complete the baseline visit assessments, will be randomized if eligible and will commence dosing, with the first dose to be taken in the morning the day after all the Baseline visit (visit 3) procedures are completed. The subject must be at least 3 years old at the time of randomization.

Randomization will be performed through an interactive website. In order to prevent age imbalance, randomization will be stratified by age with two strata, 3-4 years and 5-6 years. Block randomization will be used with random block sizes. Subjects will be assigned a study ID at the time of enrollment. The study ID includes the identification of the center and a unique subject ID. The DCC will generate a randomization table for each of the strata using a permuted block design with random block sizes. Kit numbers assigned at each local site pharmacy will be tracked at the NeuroNEXT Central Pharmacy through the interactive IWRS system. For sites using a research pharmacy, a prescription for the study drug (AFQ056 or placebo) with subject number on the prescription may be written by a licensed physician investigator on the study and exchanged at the site research pharmacy for the packet to which the subject was randomized.

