17. If a subject is withdrawn from the study during the placebo-lead in period or prior to randomization, they will be brought back in for an abbreviated follow-up/termination visit. Please refer to Section 4.3. Subject Withdrawal Criteria for more details. Subjects withdrawing early (after randomization has occurred) will complete an end of study visit at which assessments and procedures for the 16 month visit (v14) will be conducted, and then if possible will complete a follow up visit at which the same procedures as listed for the 17 month follow up visit (v15) will be conducted. If subjects discontinue study drug prior to the early termination visit, only safety outcomes are assessed during the termination visit (Blood draw, urine dipstick, EKG, vitals, physical, neurological and psychological exams, suicidality assessment, fundoscopic exam, AE review, study drug accountability) and a follow-up email or phone call to document adverse events will be completed 30 days later.
18. If the safety sample obtained at screening visit cannot be analyzed, the sample can be re-drawn at visit 2. In this case dosing can begin, but the results from the repeat blood test must be obtained and acceptable before randomization can be done at Visit 3. If a lab result is abnormal and deemed not clinically significant by the Site Investigator, dosing may proceed. If the safety samples cannot be obtained at a visit following randomization (v5, 9, 11 and 14), then the sample can be re-drawn at the next visit to the site.
19. Depending upon the timing of the visit, the evening/p.m. dose may be administered after the completion of the visit. If the visit is done earlier in the day, the family will retain the current bottle being used in order to administer the evening dose on the day of visit 3. The bottle diluted at visit 3 will then be used starting with the morning dose the day after the visit. This bottle will be then be returned at visit 4 so that site study staff may complete accountability documentation. Please see the NN107 FX LEARN MOP for details about data entry related to accountability.

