### 6.2.1 Screening/Pre-Randomization Evaluations/procedures

At the beginning of the Screening visit, informed consent to enable participation in the study will be obtained from a legally authorized representative, a parent or legal guardian, by licensed physician investigator delegated to obtain consent. Screening assessments will be completed after consent, after which the subject will receive bottles for placebo lead-in at the end of the visit. The purpose of the screening period is three-fold: to confirm eligibility before randomization, to stabilize placebo effect, and to allow a control group for the language intervention/placebo group.

If the subject does not meet eligibility criteria he/she will be discontinued before the -2 month visits (visit 2) and neither visit 2 nor the baseline visit will be completed. If eligible, the patient will complete the -2 month visit for dispensing of placebo bottle and adverse event review. The subject will be randomized during the baseline visit but will not receive new study medication until all procedures at the baseline visit have been completed. In case a baseline visit needs to be split between multiple days, baseline visits may begin up to 48 hours before the first dosing day with the medication post-randomization. Typically, the Baseline visit will occur the day before the first day of post-randomization dosing.

If a patient fails to meet an eligibility criterion that the investigator deems may change over time, such that the patient may qualify if screened again at a later date, the patient may be re-screened for eligibility. The re-screening visit must occur at least 4 weeks after the initial screening visit occurred. If a patient is re-screened, all inclusion and exclusion criteria must be reassessed prior to final eligibility determination.

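### A safety blood missed at screening may first be drawn at the baseline visit with no stated need for a result, so a child can be randomized and dosed before exclusion 7 can be assessed

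*Combined protocol and SAP*

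**What the plan says.** - **Section 4.2, exclusion 7** excludes children with "Abnormal laboratory values at screening that are in the opinion of the investigator are clinically significant and may jeopardize the safety" of the subject.
- **Section 6.3.10** schedules safety bloods at screening and at months 2, 8, 10 and 16. On a missed screening sample it says: "If the safety blood samples cannot be collected at the screening visit, sites may collect them at the -2 month or baseline visits" (visits 2 and 3), provided only that the draw precedes randomization. It sets no condition on the result. The same section sends safety samples to a central laboratory and gives no turnaround time.
- **Section 6.1, footnote 18** deals with a different failure: "If the safety sample obtained at screening visit cannot be analyzed, the sample can be re-drawn at visit 2". Lead-in dosing may start meanwhile, but "the results from the repeat blood test must be obtained and acceptable before randomization can be done at Visit 3".
- **Section 6.2.1** places randomization within the baseline visit. A baseline visit split over days may start no more than 48 hours before the first dosing day. On failures of eligibility it says: "If the subject does not meet eligibility criteria he/she will be discontinued before the -2 month visits".
- **Section 4.4.6** randomizes a child who is eligible, "with the first dose to be taken in the morning the day after all the Baseline visit (visit 3) procedures are completed".

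**The concern.** In both situations the child arrives without a usable screening laboratory result. If blood was drawn but could not be assayed, the plan insists on an acceptable result before randomization. If no blood was drawn at all, the plan asks only that a tube be filled before randomization. Nothing in the documents explains why the second case should carry the weaker condition.

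What is at stake is a safety exclusion in children aged 3 to 6. A child who meets exclusion 7 could be randomized, and in the AFQ056 arm given active drug, before anyone has seen the abnormal value. That child then either continues in breach of eligibility or becomes a withdrawal after randomization, and section 4.3 says such withdrawals will not specifically be replaced.

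**Working it through.** No figure in the plan needs reproducing. The check sets the two rules side by side and follows the timeline.

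| | Section 6.3.10 | Footnote 18 |
|---|---|---|
| Trigger | Screening safety sample not collected | Screening safety sample obtained but not analyzable |
| Latest draw offered | Visit 3 | Visit 2 |
| Condition before randomization | Sample collected | Result obtained and acceptable |
| Time from latest draw to randomization | Same visit | About 2 months (month −2 to month 0) |

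**Timeline for a first draw at visit 3.** The sample is drawn, the child is randomized during the same visit, and the first post-randomization dose is normally taken the next morning. Splitting the visit allows at most 48 hours between its start and the first dosing day. In that time the sample must be shipped, assayed, reported and reviewed. The documents give no turnaround. If it is assumed to be 1 to 5 days, a result before the first dose is possible only at the short end of that range, and no text tells the site to wait.

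**Fit with other sections.** Section 5.1 starts lead-in dosing a few days after screening, once eligibility is confirmed. Section 6.2.1 removes ineligible children before visit 2. Neither can be met on exclusion 7 when the first safety blood is drawn at visit 2 or 3.

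**Cross-reference.** In the Schedule of Activities the screening cell for Safety Labs carries marker 17, which is the note on early withdrawal. Marker 18 sits on Drug Accountability. Footnote 20 cites notes 13, 14 and 18 for assessments that may be made up later, which suggests that the Safety Labs marker should be 18.

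**Size.** A child reaches the visit 3 option only if missed at both visit 1 and visit 2. The documents give no miss rate. As an illustration, assume a rate p of 5% to 15% per visit, independent between visits:

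- Missed at both visits, per 100 children: 100 × p² = 100 × 0.05² = 0.25, up to 100 × 0.15² = 2.25.
- Allocated AFQ056 at 1:1: half of that, 0.125 to 1.125.

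Children who are hard to bleed once may be hard to bleed again, which would move the count up from p² toward p. Only those with a clinically significant abnormality would actually breach exclusion 7, and no rate for that is given.

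**The case against.** The strongest reply is that section 6.3.10 is silent about the result and does not waive it, and that other text makes randomization depend on eligibility. Section 6.2.1 gives confirming eligibility before randomization as a purpose of the screening period. Section 4.4.6 randomizes only eligible children. Section 4.4 has the coordinator confirm the criteria on the website, and inclusion and exclusion criteria are reviewed at every visit. Section 6.3.10 itself wants significant screening findings discussed before enrollment. A careful site might well wait, and the Manual of Operations or the randomization system may already enforce this. That stands as mitigation. But none of this text names a laboratory result, and a coordinator with no value has nothing on which to fail the child. The specific permission to draw at visit 3 is left intact.

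Several stronger readings are tempting, and the documents do not support them:

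- *The two rules contradict each other outright.* Their triggers differ, so this is inconsistent handling of the same missing result.
- *No pre-drug value would exist, so later abnormalities could not be attributed.* The draw must precede randomization, and section 5.1 makes the lead-in placebo. A visit 3 sample that is successfully assayed is a valid pre-drug baseline, whenever it is reported. That baseline is lost only if the sample fails, a case that neither text covers.
- *The child is titrated unobserved until the month 2 bloods.* Dose reviews are weekly. With the assumed 1 to 5 days, the result would return before the first weekly increase.
- *A large share of the trial is exposed.* A single-visit miss rate does not describe the affected group. The remark in section 6.3.10 about blood volume concerns filling all the tubes, and safety tubes are drawn first.
- *There is no route out for a late failure.* Section 4.3 already describes an abbreviated termination visit and how such a child is marked ineligible before randomization.

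Timing also matters. The synopsis ends enrollment in February 2020 and this protocol is dated 02/03/2021, so few or no randomizations may remain.

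**Conclusion.** The concern holds as a gap in the eligibility rules. A site can comply fully with section 6.3.10 and still randomize and dose a child before exclusion 7 can be assessed, although the plan's own standard for a comparable case is a reviewed result. The conclusion rests on the wording of sections 6.3.10, 6.2.1 and 4.4.6 and footnote 18, and on a shipped sample not normally being reported within the same visit. The number affected is probably small. It depends on unstated rates of missed draws at visits 1 and 2, and only the AFQ056 arm is exposed to drug. No material effect on the primary analysis is shown. The case for correcting it is that a safety exclusion can be bypassed and closing the gap is cheap.

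**What to change.** 1. Reconcile section 6.3.10, footnote 18 and section 6.2.1 so that one rule covers every late eligibility safety sample, whether never collected or not analyzable. The direct way is to extend footnote 18's existing condition to the section 6.3.10 case: result obtained and judged against exclusion 7 before randomization. The visit 3 draw need not be removed if randomization waits for the result.
2. Have the eligibility confirmation at randomization record that result.
3. Correct the Schedule of Activities so that the screening Safety Labs cell points to note 18, and check the neighboring markers.
4. In section 6.2.1, cross-refer to the pre-randomization withdrawal path in section 4.3 for children who fail on a late result.
5. If randomization is already complete, identify any child whose first safety result postdates randomization and report it.

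The cost is protocol wording, one eligibility check, an occasional delay to randomization and, for item 5, a comparison of dates already held.

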### **6.3.11 Pharmacokinetic Studies**

Pharmacokinetic assessment will be done for AFQ056 for all patients at screening, 2, 8, 10, and 16 month visits (visits 1, 5, 9, 11, and 14) by collecting blood for PK after safety labs are drawn. Blood samples will be drawn prior to dosing of the PM AFQ056 dose. The date and time of blood collection will be recorded on the PK blood collection page in the source documents and CRF, together with the date and time for the past three doses and the time of the last meal immediately preceding the PK sampling time.

If the PK blood samples cannot be collected at the screening visit, sites may collect them at the -2 month or baseline visits (v2 or v3) as long as it is prior to randomization. If the PK blood samples cannot be obtained at a visit occurring post-randomization (v5, 9, 11 and 14), then the samples may be collected at the next visit to the site.

PK Samples from all sites will be batched and shipped twice, in shipments midway through the study, and at the end of the study. The study sites will be notified by the Study Team site when to prepare and ship samples. The CCC Central Lab will provide tubes and materials for PK collection from subjects, shipping materials, labels, and a Fed Ex account number for shipping PK tubes from sites to the CCC Central lab. One batch of tubes will be shipped to the CCC Central Laboratory at University of Rochester in batches from each study site midway through the study and at the end of the study. The second batch of tubes will be held at the site until the CCC Central Laboratory notifies the site that the first batch of tubes have arrived and been inventoried and stored. After the notification, the sites will then ship the corresponding second batch of tubes to the CCC Central Laboratory.

After all samples have been collected and received from the sites, the CCC Central Laboratory will ship them internationally to Veeda lab analysis of AFQ056 levels. Veeda was identified by Novartis and has been used for PK measurements to quantify AFQ056 in plasma samples for previous Novartis studies.

All samples will be given a unique sample number (NeuroNEXT Subject ID) as listed in a PK log. Documentation of PK sample logs and shipping will be maintained in the source documents at study sites and in the lab records for the study at the CCC Central Laboratory. After assay, PK values will be sent directly from Veeda Laboratory to the NeuroNEXT DCC via an established data transfer mechanism. These values will not be visible to the sites to avoid unblinding.

